TNBC Triple Negative Breast Cancer TBIL Total Bilirubin TNM Tumor Nodes Metastasis	Subj FU	Subject Follow Up
TNBC Triple Negative Breast Cancer TBIL Total Bilirubin TNM Tumor Nodes Metastasis	SUL	-
TBIL Total Bilirubin TNM Tumor Nodes Metastasis	TNBC	Triple Negative Breast Cancer
TNM Tumor Nodes Metastasis		

WHO	World Health Organization
WHO-DD	WHO Drug Dictionnary

TPL N°: eTPL SA-02-01 Of SOP SA-02.08 TPL Effective Date: 31 Mar 2016 Approved in Vault: 07 Mar 2022

#### 2. Introduction

This Statistical Analysis Plan was written for the clinical trial GCT1029-01 conducted in a maximum of five to ten sites in Spain, United Kingdom and the US, with up to 20-30 additional sites to be included in Europe. The ICH guideline E3 "Structure and Content of Clinical Study Reports" was used as a guide to the writing of the plan.

## 3. Trial Design and Objectives

The present SAP covers the escalation part only as the expansion part of the trial was not initiated.

## 3.1 Trial Objectives

## 3.1.1 Primary Objectives

- To determine the Maximum Tolerated Dose (MTD) and/or the Recommended Phase 2 Dose (RP2D) of GEN1029.
- To establish the safety profile of GEN1029.

## 3.1.2 Secondary Objectives

- To establish the pharmacokinetic (PK) profile and evaluate immunogenicity of GEN1029 after single and multiple infusions.
- To evaluate the antitumor activity of GEN1029.

## 3.1.3 Exploratory Objectives

- To assess biomarkers predictive of response or resistance to GEN1029.
- To assess potential pharmacodynamic biomarkers of GEN1029.
- To assess the metabolic response in tumors.

#### 3.2 Trial Design

The trial design details are available in section 4 Trial Design of the protocol final version 9.0 dated 24 October 2019.

Unless other events, subjects are intended to receive GEN1029 until PD. Note that the treatment may be stopped due to other reasons.

In the dose escalation part, up to 3 dose regimens were evaluated:

- The Biweekly Regimen: subjects are dosed once every 14 days (Q2W)
- The Priming Regimen: in the first cycle, subjects receive a priming dose; after 14 days and thereafter, they are dosed with the full dose once every 14 days (Priming/Q2W).
- The Intensified Regimen (protocol v8.0): 8xQ1W/Q2W: subjects are dosed every week for the first 8 weeks and then they are dosed once every 14 days.

F

Page 7 of 44

TPL N°: eTPL SA-02-01 TPL Version: 02 Of SOP SA-02.08

For the assessments of each cohort the dose limiting toxicities (DLT) will be collected for the first two cycles i.e. DLT period of 28 days.

The dose escalation part will be performed as a modified Bayesian Optimal Interval (mBOIN) design.

More details can be found in section 4.3 of the protocol final version 9.0 dated 24 October 2019.

## 3.3 Sample Size Justification

The protocol v9.0 planned to enroll up to approximately 100 subjects shared between the Regimens. As the MTD was found earlier than the highest dose level planned in the protocol and the expansion will not be initiated, only 48 subjects will be recruited.

Of those 48 subjects:

Page 8 of 44

TPL N°: eTPL SA-02-01 Of SOP SA-02.08 TPL Effective Date: 31 Mar 2016

- Two subjects were assigned to the priming regimen:
- One received the priming dose and then continued on a lower dose level. This subject is considered as treated on the 'biweekly regimen'.
- The second subject received the priming dose and continued with a higher dose level, this subject will be analysed as treated in the priming regimen.
- Three subjects were also planned in an Intensified Regimen (8xQ1W/Q2W) all of whom experienced DLTs and, consequently, this dosing regimen was permanently discontinued.

The Intensified Regimen was discontinued per protocol v9.0.

More details on sample size can be found in section 11.8 Sample Size Calculation of the protocol final version 9.0 dated 24 October 2019.

## 4. General Analysis Definitions

Data will be analyzed using SAS (Version 9.4 or higher). For graphs R (RStudio, Version 3.5.0 or higher) can be used in addition.

Depending on the nature of the reported endpoint, the following type of summary statistics will be used:

- Categorical data will be summarized in contingency tables presenting frequencies and percentages. Response rates will be presented as the number and percentage of subjects including exact 95% confidence interval using the Clopper-Pearson method.
- Continuous data will be summarized using number of non-missing values (n), mean, standard deviation, median, 25th and 75th percentiles, minimum and maximum values.
- Time to event parameters will be summarized using Kaplan-Meier estimates: median time, first and third quartiles along with approximate 95% confidence intervals (the default conftype=loglog in proc lifetest will be used). The 3, 6, 9, 12 and 24 month event-free rates will also be presented together with the 95% confidence intervals.

In general, in plots where subject data are grouped together (e.g. plots of means), the ticks on the time-axis will denote the nominal visit numbers (e.g. Scr, C1D1, C1D2 etc.) separated with distances proportionate to the difference between the time-points of the corresponding visits in the relevant dose level (cf. the Visit Number and Day/Week rows of table of assessments in section 1 Visit Schedule of the protocol final version 9.0 dated 24 October 2019).

Unscheduled visit data will not be tabulated unless otherwise specified. In plots where individual subject data are plotted vs. time, the time on the horizontal axis will denote the actual time since C1D1. Unscheduled visit data will be included in these plots.

In tables and listings presenting data by visit, the visit labels (Screening, Cycle 1 Day 1, Cycle 1 Day 2, ..., End of Treatment, Safety Follow-up, Subject Follow-up and End of Trial, Unscheduled) or their abbreviated term (Scr, C1D1, C1D2, ..., EOTrt, Saf FU, Subj FU, EOTrial, UNS) will be used.

In tables and listings presenting coded data (e.g. medical history, concomitant medication, adverse events ...), the dictionary and the version used will be mentioned in the footnote.

Page 9 of 44

TPL N°: eTPL SA-02-01 Of SOP SA-02.08 TPL Effective Date: 31 Mar 2016

In tables and listings displaying derived endpoints based on RECIST v1.1, this RECIST version will be mentioned in the output.

Version: 2.0

#### 4.1 Trial Period and Visit Window Definitions

#### 4.1.1 Trial Periods

Screening period will be defined as the period between signature of the ICF and the date of first IMP administration.

On-Treatment period will be defined as the period between first IMP administration (included) and last IMP administration, including the safety follow-up period (taking the maximum of date of last IMP +70 days, end of treatment visit and safety FU visit).

Follow-up period will be defined as the period after the On-Treatment period (that includes the safety FU period) +1 day until the date of last contact.

## 4.1.2 Visit Windows

Visit windows are defined in the protocol. Those will not be used in the analysis to avoid excluding important data due to dates outside visit windows. Tables will assume that observations are from the recorded visit irrespective of the date specified.

### 4.2 Planned Analyses

Safety results will be summarized for the DMC after each cohort in the dose escalation part.

The final analysis of trial data will be performed when the trial is completed and will be based on all subject data of the dose escalation part.

The final analysis will be based on locked database with clean data. A full integrated clinical trial report will be produced when the trial is completed.

#### 4.3 Definition of Populations (Analysis Sets)

Populations will be finalized at the pre-database lock meeting.

## 4.3.1 Full Analysis Set

The Full Analysis Set (FAS) consists of all subjects who received at least one dose of GEN1029. Subjects will be analyzed according to the actual trial treatment received. The FAS and the Safety Set (SAF) are defined the same way.

### 4.3.2 Safety Set

The Safety Set (SAF) consists of all subjects who received at least one dose of GEN1029. Subjects will be analyzed according to the actual trial treatment received. The FAS and the Safety Set (SAF) are defined the same way.

## 4.3.3 Dose-Determining Set

The Dose-Determining Set (DDS) consists of all subjects from the Safety Set who either have received between 80% and 125% of the planned dose and have completed the DLT observation period (day 1-28), or have experienced a DLT during cycle 1. This constitutes an evaluable subject for the determination of MTD Statistical Analyses. Subjects with a

Page 10 of 44

TPL N°: eTPL SA-02-01 Of SOP SA-02.08 TPL Effective Date: 31 Mar 2016

Approved in Vault: 07 Mar 2022

dose reduction (below 80% of the planned dose) due to abnormal ALT/AST measurements will also be considered evaluable for MTD and be included in the DDS.

Version: 2.0

Details of the analysis sets definition will be included in a separate document, the "Classifications of Analysis Populations" plan.

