1 VISIT SCHEDULE

1.1 Dose Escalation Part

In the dose escalation part, up to 2 dose regimens may be evaluated:

- The Biweekly Regimen: patients are dosed once every 14 days (Q2W).
- The Priming Regimen: in the first cycle, patients receive a priming dose. After 14 days and thereafter, they are dosed with the maximum starting dose once every 14 days (Priming/Q2W).

An overview of the dosing frequency as well as treatment cycle duration and dose limiting toxicity (DLT) period duration, and scanning frequency is shown in Figure 1-1. A cycle is always 14 days and the DLT period is always 28 days, irrespective of which dose regimen the patients are following.

Further details on when the 2 dose regimens will be available and open for enrollment are described in Section 4.2.

Table 1-1 lists all of the assessments in the dose escalation part and indicates with an "X" the visits at which they are performed. All data obtained from these assessments must be supported in the patient's source documentation.

Table 1-2 shows the timing of the ECG assessments, Table 1-3 shows the timing of the PK sampling, Table 1-4 shows the timing of cytokine and complement sampling, and Table 1-5 shows the timing for measurement of vital signs in relation to infusions.

*: Mandatory PET-CT scans must be taken at screening and, if avid at screening, also at Cycle 2 Day 2, and week 12 (±7 days). If PET-CT at screening showed no avidity, a CT scan has to be done instead of a PET-CT in week 12 (±7 days).

: A CT scan must be performed at Cycle 3, Day 8-14 after first dose. From week 18 (\pm 7 days) until week 50 after first dosing, CT scans must be performed every 6 weeks (\pm 7 days), and every 12 weeks (\pm 7 days) thereafter. Imaging assessments should follow calendar days and should not be adjusted for delays in cycle starts. *: Only if a patient, who has been exposed to GEN1029, did not have any PET-CT scans while on treatment and displayed avidity at screening.

Figure 1-1 Overview of Dosing and Scanning Frequency, DLT and Cycle Duration – Dose Escalation Part

Treatment Cycle	Screening	Cycle 1-3 ¹			Cycle 4-PD ¹ End of treatment ²		Safety Follow-up ²¹		Patient follow-up	End of trial	Unscheduled		
Day	≤21 days prior to Visit C1-D1	1d	2d	3d ^{24,28}	8d	1d	8d ²²	-	30 days after last dosing	70 days after last dosing	13W, 26W, 39W + 52W after last dosing	-	-
Visit window ³		±1d	-	-	±1d	±3d	±1d	-	±7d	±7d	±14d	-	-
Informed Consent ⁴	Х												
Eligibility Criteria	Х												

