4.3 Dose Escalation Part

In the dose-escalation part, there will be a minimum of 2 nights between the first and second patient in each dose cohort to account for any safety signals at each new dose level. This might be modified according to recommendations from the DMC and as endorsed by the sponsor safety committee. In addition, the first cohort of the Biweekly Regimen will be a single patient cohort. Furthermore, no other patients within a dose cohort will receive their first treatment simultaneously, i.e. on the same day, during the dose escalation part of the trial, unless apparently efficacious dose levels which are declared safe by the DMC are further investigated. During treatment, safety assessments will initially be performed on a weekly basis. For the assessments of each cohort, the DLTs will be collected for the first two cycles i.e. DLT period of 28 days. For the priming regimen, the DLT period must contain 14 days evaluation of one full dose administered after the priming dose have been administered. A patient is defined as "evaluable" if a DLT is observed prior to completing the DLT period, or if the DLT period is completed without any DLTs.

The dose escalation part will be performed as a mBOIN design (Yuan et al., 2016). This is in many ways similar to a traditional 3+3 design (even more similar to its 3+3+3 variant) except that the mBOIN design may allow re-escalation to an already investigated dose level. Re-escalation is allowed when the previous dose level is considered safe (based on data from additional patients). Re-escalation is not allowed to dose levels that have been terminated.

Specifically for this trial a target toxicity level of 30% has been chosen leading to escalation and de-escalation borders of lambda1=0.24 and lambda2=0.36.

According to the mBOIN design each time a cohort of patients has been completed, it is evaluated whether the next cohort should stay on the same dose, escalate to the dose level above or deescalate to the dose level below. This evaluation is based on the frequency of DLTs on the current dose level in the following way:

•	DLT frequency at current dose level ≤ 0.24 :	Escalate
•	DI frequency at current dose level >0.24 and <0.36 :	Stay at same dose level

De-escalate

• DLT frequency at current dose level >= 0.36:

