7.1 Dose-limiting Toxicity

For the purpose of dose escalation, SAEs, non-serious (NS) \geq grade 3 AEs and clinically significant abnormal lab values will be collected and assessed by the DMC for DLTs (in each cohort during the first two cycles; i.e. DLT period of 28 days). National Cancer Institute (NCI) Common Terminology Criteria for Adverse Events (CTCAE) v.4.03 will be used to grade the intensity of adverse events.

DLT criteria are defined below:

Hematological

- Grade 4 neutropenia (i.e., ANC $< 0.5 \times 10^9$ cells/L) for minimal duration of seven days.
- Grade 3 and 4 febrile neutropenia (i.e., $ANC < 1.0 \times 10^9$ cells/L with a single temperature of > 38.3°C or a sustained temperature of ≥ 38°C for more than one hour).
- Grade 4 thrombocytopenia ($\leq 25.0 \times 10^9$ platelets/L) for minimal duration of seven days.
- \geq Grade 3 thrombocytopenia associated with bleeding.
- Grade 4 anemia.

Note: Any grade 4 hematological AE should be checked 2x/ week for up to 4 weeks until a repeated value below grade 2 is reported.

Non-hematological

- Grade 4 infusion-related reactions.
- Grade 4 anaphylaxis.
- Grade 3 infusion-related reactions that do not resolve to \leq grade 1 within 24 hours.
- At least possibly related grade 4 AST, ALT or bilirubin elevations.
- At least possibly related grade 3 AST, ALT or bilirubin elevations that do not resolve to \leq grade 1 within 7 days.
- At least possibly related AST, ALT or bilirubin elevations by more than one grade from baseline (e.g. grade 0→grade 2 as defined in the NCI-CTCAE Version 4.03) that do not resolve to ≤ grade 1 within 7 days.
- At least possibly related \geq grade 2 AST or ALT elevations with concomitant bilirubin >2.0×ULN with no signs of cholestasis, i.e. a Hy's law case.
- Re-occurring of at least possibly related AST, ALT or bilirubin elevations ≥ grade 3, observed in cycle 1 and again in cycle 2 independent of resolution.
- At least possibly related ≥ grade 3 amylase and/or lipase elevations with significant clinical symptoms that do not resolve to ≤ grade 1 or baseline within 7 days.
- Grade \geq 3 diarrhea that does not respond to optimal antidiarrheal treatment within 2 days
- Grade \geq 3 vomiting that does not respond to optimal antiemetic treatment within 2 days
- Grade 3 nausea that does not respond to optimal antiemetic treatment within 7 days

- Any ≥ grade 3 at least possibly related non-hematological AE, which occurs during the first two cycles *excluding*:

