11.1.4 Dose-Determining Analysis Set

The Dose-Determining Set (DDS) consists of all patients from the safety set who either have received between 80% and 125% of the planned dose and have completed the DLT observation period, or have experienced a DLT during cycle 1. This constitutes an evaluable patient for the determination of MTD Statistical Analyses.

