11.4.1.1 Primary Endpoints

- Number of DLTs during the DLT period (initial 28 days of treatment). See Section 4.3 for how the MTD will be determined.
- Summary tables for adverse events (AEs) will include only AEs that started or worsened during the on-treatment period, the treatment-emergent AEs.

The incidence of treatment-emergent adverse events (new or worsening from baseline) will be summarized by System Organ Class (SOC) and or Preferred Term (PT), severity (CTCAE grade), type of adverse event, and relationship to IMP.

SAEs, non-serious AEs and AEs of special interest (AESI) during the on-treatment period will be tabulated.

All deaths (on-treatment and post-treatment) will be summarized.

All AEs, deaths and SAEs (including those from the pre and post-treatment periods) will be listed and those collected during the pre-treatment and post-treatment period will be flagged.

Further summaries of AEs will be specified in the statistical analysis plan.

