## 17.1 Primary Endpoint: Dose-limiting Toxicities (DLT)

DLT definition is provided in protocol V9.0 section 7.1.

All analyses on the primary endpoint will be done on the dose-determining set in the dose escalation part of the trial.

The number of subjects with a DLT will be presented for each dose-level. All the DLT information will be included in a graph marking subjects who have no DLT and have a DLT in order of inclusion, also indicating the subjects which are not evaluable for DLT (not part of the DDS).

Subjects excluded from the DDS and the reasons will be listed.

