Table 14.02.01.03	Disease Response According to RECIST 1.1 – All Responses	Full Analysis Set
Table 14.02.02.01	Time to Confirmed Response According to RECIST 1.1	Full Analysis Set patients with Confirmed CR or PR
Table 14.02.02.02	Progression Free Survival According to RECIST 1.1	Full Analysis Set
Table 14.02.02.03	Duration of Confirmed Response According to RECIST 1.1	Full Analysis Set patients with Confirmed CR or PR
Table 14.02.03.01	Overall Survival	Full Analysis Set
Pharmacokinetics		
Table 14.02.04.01	Plasma/Serum Concentration of Hx-DR5- 01- Descriptive Statistics	PK Analysis Set
Table 14.02.04.02	Plasma/Serum Concentration of Hx-DR5- 05- Descriptive Statistics	PK Analysis Set
Table 14.02.05.01	PK Parameters of Hx-DR5- 01 – Descriptive Statistics	PK Analysis Set
Table 14.02.05.02	PK Parameters of Hx-DR5- 05 – Descriptive Statistics	PK Analysis Set
Table 14.02.06.01	PK Parameters of Hx-DR5- 01 by ADA Positivity	Immunogenicity Set
Table 14.02.06.02	PK Parameters of Hx-DR5- 05 by ADA Positivity	Immunogenicity Set
Table 14.02.7	Immunogenicity of GEN1029	Immunogenicity Set
Safety Evaluation		
Table 14.03.01	Primary Endpoint: Summary of DLT	Dose-Determining Set
Table 14.03.02	GEN1029 Administration – Extent of Exposure	Safety Set
Table 14.03.03	Summary of Treatment Emergent Adverse Events	Safety Set
Table 14.03.04.01	Treatment Emergent Adverse Events – by Preferred Term	Safety Set
Table 14.03.04.02	Treatment Emergent Adverse Events – by Preferred Term and Cycle	Safety Set
Table 14.03.04.03	Treatment Emergent Adverse Events - by SOC and Preferred Term	Safety Set
Table 14.03.04.04	Treatment Emergent Adverse Events - by SOC and Preferred Term and CTCAE Grade	Safety Set
Table 14.03.05.01	GEN1029 Related Treatment Emergent Adverse Events - by Preferred Term	Safety Set
Table 14.03.05.02	GEN1029 Related Treatment Emergent	Safety Set

	Adverse Events - by	
Table 14.03.05.03	Preferred Term and Cycle GEN1029 Related Treatment Emergent	Safety Set
	Adverse Events - by SOC and Preferred Term	
Table 14.03.05.04	GEN1029 Related Treatment Emergent	Safety Set
	Adverse Events – by SOC and Preferred Term and CTCAE Grade	
Table 14.03.06.01	Treatment Emergent Adverse Events Grade ≥3 - by Preferred Term	Safety Set
Table 14.03.06.02	Treatment Emergent Adverse Events Grade ≥3 - by Preferred Term and Cycle	Safety Set
Table 14.03.06.03	Treatment Emergent Adverse Events Grade ≥3 - by SOC and Preferred Term	Safety Set

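### The Dose-Determining Set counts a DLT as grounds for entry only in cycle 1, although the DLT period covers two cycles, so some cycle-2 DLTs can drop out of the primary DLT table

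*SAP*

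**What the plan says.** Both documents use a two-cycle DLT window. Protocol 1.1 states: "A cycle is always 14 days and the DLT period is always 28 days". SAP 3.2 likewise collects DLTs over the first two cycles. The primary endpoint in Protocol 11.4.1.1 begins "Number of DLTs during the DLT period (initial 28 days of treatment".

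The documents then give two different rules for who is evaluable.

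- Protocol 4.3, which governs the escalation, counts a patient as evaluable "if a DLT is observed prior to completing the DLT period, or if the DLT period is completed without any DLTs".
- Protocol 11.1.4, which defines the Dose-Determining Set (DDS), takes patients with 80% to 125% of the planned dose who "have completed the DLT observation period, or have experienced a DLT during cycle 1".
- SAP 4.3.3 repeats the second rule with small additions: "have completed the DLT observation period (day 1-28), or have experienced a DLT during cycle 1". It also keeps patients whose dose fell below 80% because of abnormal ALT or AST.

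SAP 17.1 makes the DDS the population for the primary endpoint: "All analyses on the primary endpoint will be done on the dose-determining set". The output is Table 14.03.01, "Primary Endpoint: Summary of DLT". SAP section 5 records the ALT/AST addition as a departure from the protocol but says nothing about the cycle-1 limit.

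**The concern.** Days 15 to 28 are half of the DLT window, and a DLT in that half does not by itself bring the patient into the set on which DLTs are counted. Nothing in the endpoint supports the limit. One criterion in Protocol 7.1, recurrence of liver-parameter elevations of grade 3 or higher in cycle 2 after cycle 1, cannot be met until cycle 2. For a patient with incomplete dosing or follow-up, a DLT on Day 14 counts and the same DLT on Day 15 need not.

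An excluded patient has, by construction, had the event being counted. The bias can therefore go only one way, towards a lower reported DLT rate. The primary table could also disagree with the patient record that fed the mBOIN algorithm, because that algorithm uses the Protocol 4.3 rule.

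**Working it through.** **1. Scale.** The plan's own decision limits are 0.24 and 0.36 at a 30% target. With φ = 0.30, and assuming p1 = 0.6φ = 0.18 and p2 = 1.4φ = 0.42 (not stated in the documents):

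- λ1 = ln[(1−p1)/(1−φ)] / ln[φ(1−p1)/(p1(1−φ))] = ln(0.82/0.70) / ln(0.246/0.126) = 0.2365
- λ2 = ln[(1−φ)/(1−p2)] / ln[p2(1−φ)/(φ(1−p2))] = ln(0.70/0.58) / ln(0.294/0.174) = 0.3585

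These round to the stated limits. All decision counts in Protocol Table 4-3 for 3 to 9 patients also reproduce. The design figures are not in dispute.

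**2. Window.** 2 cycles × 14 days = 28 days. Entry by DLT covers Days 1 to 14 only.

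**3. Patients with a cycle-2 DLT under SAP 4.3.3.**

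| Situation | In the DDS? | Evaluable under Protocol 4.3? |
|---|---|---|
| 80-125% of planned dose, followed to Day 28 | Yes, by completion | Yes |
| Under 80% because of an ALT/AST reduction | Yes, by the added clause | Yes |
| Died, withdrew or lost before Day 28 | No | Yes |
| Under 80% for another reason | No | Yes |

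**4. A route to the last row that the protocol itself contains.** Protocol 7.1 lists "Grade 4 infusion-related reactions" and grade 4 anaphylaxis as DLTs. Protocol 7.2.2.2 requires the drug to be stopped at once and for good when they occur. Footnote 3 to Table 1-1 allows at most two doses in the 28 days. Let f be the share of the cycle-2 infusion given. If planned dose means the sum of the two infusions, the patient received (1 + f)/2 of it, and (1 + f)/2 < 0.80 when f < 0.60. If it is judged per infusion, the cut is f < 0.80. The SAP does not say which applies. A patient under the cut is excluded even if followed to Day 28.

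**5. Effect of losing one such patient.** The count x/n becomes (x−1)/(n−1), a fall of (n−x)/[n(n−1)].

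| All DLTs counted | One DLT patient dropped | Change (points) | Crosses 30%? |
|---|---|---|---|
| 1/3 = 33.3% | 0/2 = 0% | −33.3 | Yes |
| 1/6 = 16.7% | 0/5 = 0% | −16.7 | No |
| 2/6 = 33.3% | 1/5 = 20.0% | −13.3 | Yes |
| 3/6 = 50.0% | 2/5 = 40.0% | −10.0 | No |
| 1/9 = 11.1% | 0/8 = 0% | −11.1 | No |
| 2/9 = 22.2% | 1/8 = 12.5% | −9.7 | No |
| 3/9 = 33.3% | 2/8 = 25.0% | −8.3 | Yes |
| 4/9 = 44.4% | 3/8 = 37.5% | −6.9 | No |

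The 30% line is a relevant reference because Protocol 4.3 requires the RP2D to have an observed DLT rate below it. By Table 4-3, 3/9 and 2/8 both mean stay, so in that case only the reported rate changes.

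**The case against.** The case for treating this as a minor wording point is reasonable.

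- **Few patients can be affected.** Protocol 7.3 continues observation to the end of the cycle after a stop, and Protocol 8.3 schedules visits 30 and 70 days after the last dose. Planned follow-up therefore passes Day 28. Protocol 6.4.1 describes the main toxicity, transaminase elevation, as mostly a first-dose effect, and the ALT/AST clause partly covers it.
- **The infusion-reaction route is narrow.** It needs a grade 4 event early in the second infusion. Protocol 10.1.4 also counts reactions starting up to 24 hours after the infusion, when the full dose is in. If planned dose means the assigned dose level, the dosing condition might be met after all.
- **The counts 1/3 and 2/6 are not usual end states.** Both mean stay, so another cohort would normally follow.
- **No dose decision hangs on the table.** SAP 3.3 says the MTD has been found, and the expansion part was not opened.
- **The DLT stays visible.** SAP 17.1 requires a graph of all DLT information and a listing of DDS exclusions with reasons. DLTs also have their own listing.
- **A separate populations plan may settle it.** SAP 4.3.3 refers details there, and SAP 4.3 leaves populations to be finalised at the pre-lock meeting.

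These points limit the size and the consequence, and they stand to that extent. They do not repair the rule. Scheduled visits do not help a patient who dies, withdraws or is lost, and no reading of planned dose changes that group. The populations plan was not available for this review. It is meant to supply detail and should not have to overrule what the SAP states. Listings show the event, but the primary count and its denominator would still be wrong.

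**Conclusion.** The concern holds. SAP 4.3.3 and Protocol 11.1.4 state an entry rule that conflicts with the 28-day endpoint and with evaluability in Protocol 4.3. Followed as written, it can remove DLT patients from the primary table, and the reported rate can then only be too low or unchanged.

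The size is unknown. The documents do not say how many DLTs fell in cycle 2 or how many of those patients left early or were under-dosed, and the answer may be none. For one affected patient at a dose level of 3, 6 or 9 patients, the fall in the counts tabulated above is between 6.9 and 33.3 points. It crosses the 30% target only from 1/3, 2/6 or 3/9. These are illustrations, not estimates.

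The effect is confined to reporting. Cohort decisions followed Protocol 4.3, and SAP 4.5 puts the priming and intensified regimens in listings only. The point should be fixed because this is the primary-endpoint population and SAP 4.3.3 itself calls it the evaluable set for MTD analyses. It does not call the dose decisions into question.

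**What to change.** In SAP 4.3.3, replace the cycle-1 condition with: *have experienced a DLT during the DLT observation period (Day 1-28), irrespective of dose received or completion of Day 28*. Record this in SAP section 5, beside the DDS change already listed there, as a departure from Protocol 11.1.4 that brings the set into line with Protocol 4.3. Carry the same wording into the Classifications of Analysis Populations plan and produce Table 14.03.01 on that set.

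The cost is one phrase, one line in section 5, matching text in the populations plan and a re-derived population flag. No new data and no protocol amendment are needed. The pre-database-lock meeting at which populations are finalised is the natural time to do it.
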